1.43 Clinical Pharmacokinetics and pharmacodynamics

Clinical Pharmacokinetics

The PK data of AZD1775 following a single oral administration showed a moderate rate of absorption with a Tmax occurring at 3 to 4 hours. Post-peak plasma concentrations declined essentially in a mono-exponential manner with a t1/2 in the region of 10 hours. Exposure as measured by maximum plasma drug concentration observed (Cmax) and area under the curve (AUC $0-\infty$) increased in a dose-proportional manner over the dose range of 325 to 1300 mg. The urinary excretion of AZD1775 was investigated after single-oral-dose monotherapy at 325, 650, and 1300 mg of AZD1775. The mean percent of total AZD1775

excreted unchanged in urine over a 24-hour period was 5.15% to 11.9%, which is comparable to what was observed in preclinical species (urinary excretion as unchanged drug in rats and dogs were ~8.6% and 11.8% of the dose, respectively, over a 48-hour collection interval). The mean renal clearance of AZD1775 at 325 mg was approximately 2.30 L/hour (38.3 mL/minute), below that expected due to filtration alone (based on an AZD1775 unbound fraction of 39.5% and a typical glomerular filtration rate of 120 mL/minute) of 47.4 mL/minute, indicating that net reabsorption appeared to be taking place. Overall, the results suggest that urinary excretion is not the major route of AZD1775 elimination

Following single (100 to 325 mg) and multiple dose administrations of AZD1775 (25 to 325 mg BID and 100 to 200 mg once daily [QD]) with carboplatin, cisplatin, and gemcitabine, plasma exposure of AZD1775 was consistent with predictions based on the single-dose regimen. The median Tmax values were between 1.02 and 4.25 hours. Given a t1/2 of approximately 10 hours, steady-state was expected to be achieved after approximately 3 days of AZD1775 treatment in adult patients. Accumulation ratios for AZD1775 BID doses (geometric mean ratio = Day 3/Day 1) for the area under the plasma-concentration time curve from time 0 to 8 hours post dose (AUC_{0-8hr}), Cmax, and plasma drug concentration observed at 8 hours post dose (C_{8hr}) averaged 0.991 to 3.82, 0.928 to 3.32, and 1.01 to 2.98, respectively, across tested AZD1775 BID doses in combination with gemcitabine, cisplatin, and carboplatin.

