 - 6.39d2 After the patient has been registered into the study, the values of the grouping factors will be recorded. An elderly newly diagnosed AML patient will be allocated to arm A. A relapsed/refractory AML or HMA failure MDS patient will be randomized to treatment group arm B or arm C.
 - Elderly (age 60+) newly diagnosed AML patients assigned to Arm A: AZD1775 days 1-5, 8-12 and AraC days 1-5, 8-12
 - Relapsed/Refractory AML and HMA failure MDS patients randomized to Arm B: AZD1775 days 1-5, 8-12 and AraC days 1-5, 8-12 or Arm C: AZD1775 days 1-5, 8-12, 15-19, 22-26.

All patients must be registered within 14 days before starting therapy or within 72 hours after starting treatment if over a weekend or holiday. If therapy must be started when the MCCC Registration Office is closed, a telephone call must be made when the MCCC Registration Office is open as indicated above. Under no circumstances will non-registered patients be retrospectively eligible for the study.

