14.0 Body Fluid Biospecimens

Body Fluid Biospecimen Submission

14.1 Summary Table of Research Blood and Body Fluid Specimens to be Collected for this Protocol

Correlative Study (Section for more information)	Mandatory or Optional	Blood or Body Fluid being Collected	Type of Collection Tube (color of tube top)	Volume to collect per tube (# of tubes to be collected)	Baseline	Cycle 1 Day 2 (+1 Day)	Cycle 1 Day 5 (+1 Day)	Cycle 2 Day 5 (+1 Day) & Day 5 of Subse quent Odd Cycles	At time of bone marro w after cycles 1 (AML only), 2 and 4 ³	EOS	Proces s at site? (Yes or No)	Temperature Conditions for Storage /Shipping
Biomarkers	Mandatory	Whole Blood	1 x Red top 2 x Na Heparin Green top	10 mL (3)	X	X ¹			Х	X	Yes	Cold Pack
Biomarkers	Mandatory	Bone marrow aspirate	Hepariniz ed Green top	10 mL (2)	X ⁴				X	X^2	Yes	Cold Pack
Buccal swab	Optional	Saliva	n/a	n/a	Х						No	ambient
Pharmacokin etics	Mandatory	Plasma	Lavender Top	2 ml			Pre- Dose, 1, 2, 4, 6, & 8 hrs post- dose	Pre- Dose			Yes	-20°C

1. Only to be done in those patients with circulating tumor cells in their blood

- MCCC
- 2. End of study bone marrow sample is optional and to be collected only if bone marrow performed as part of patient's standard of care.
- 3. Bone marrow aspirates will be done at times of standard clinical marrow tests. Follow Tables 4.1. (AML) and 4.2. (MDS) for study schedule. In brief after cycle 1 (for AML only, at physician's discretion can be omitted, see Table 4), after cycles 2 and 4, and then at physician discretion.
- 4. This is only mandatory IF a BM biopsy has not been done within 4 weeks of study start.

NOTE: marrow bisopies will not be done soley for the purpose of drawing a research sample, but should be performed to coincide at times of standard clinical marrow biopsies/aspirates.

- 14.2 Collection and Processing
 - 14.21 Biomarkers: Process on site per lab manual. Send all samples in original tubes to lab per section 14.32.

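### The Cycle 1 PK profile may slip only to Day 6, which has no AZD1775 dose on the main schedule of any arm, so the 1 to 8 h post-dose samples cannot be validly taken there

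*Combined protocol and SAP*

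**What the plan says.** Table 14.1 (Section 14.0) lists a mandatory plasma PK collection in the column headed "Cycle 1 Day 5 (+1 Day". The samples in that cell are "Pre- Dose, 1, 2, 4, 6, & 8 hrs post- dose". The allowance runs forward only; no earlier day is permitted.

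The next column, "Cycle 2 Day 5 (+1 Day) & Day 5 of Subse quent Odd Cycles", asks for a pre-dose sample only. As printed, the +1 day there belongs to Cycle 2; the later odd cycles carry no window.

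Section 6.39d2 gives the dosing days:

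- Arm A: "newly diagnosed AML patients assigned to Arm A: AZD1775 days 1-5, 8-12 and AraC days 1-5, 8-12".
- Arm B: "randomized to Arm B: AZD1775 days 1-5, 8-12 and AraC days 1-5, 8-12".
- Arm C: "Arm C: AZD1775 days 1-5, 8-12, 15-19, 22-26".

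Sections 7.2, 7.3 and 16.1 give the same days. The footnotes in Sections 7.21 and 7.22 permit days 1-10 as an alternative in Arms A and B; Section 7.3 offers no such alternative for Arm C. The definitions under the table in Section 8.3 say that omitted doses are not made up, while held or delayed doses can be made up within the cycle.

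Neither Table 14.1 nor Section 14.22 ties the +1 day to the day 1-10 alternative, or says what to do when Day 6 has no dose.

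**The concern.** A sampling window should cover days on which the sampled event can occur. Here the event is an AZD1775 dose, and the one day of tolerance falls on the first day of the dosing gap. A site that uses the tolerance exactly as written on the main schedule has two outcomes. It may have no dose from which to time the post-dose draws and so lose the profile, or it may draw at the usual clock times and record an elimination tail as if it were a 0-8 h profile.

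The protocol fixes no weekday for Day 1, so the tolerance may well be used. With a Wednesday start, for example, Day 5 is a Sunday and the permitted shift lands on Monday, Day 6.

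At stake is objective 2.31, the pharmacokinetics of AZD1775 alone and with AraC. Section 16.61 summarises PK descriptively, with no model that would correct a mistimed series. The comments after the dose table in Section 8.12 leave open whether peak level or sustained exposure matters more for disease control, and a series without a peak cannot inform that question.

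**Working it through.** The plan states no figure to reproduce here. The check has three steps.

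**Step 1. Compare the window with the dosing calendar** (Sections 6.39d2, 7.2, 7.3).

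| Schedule | Dose on Day 5 | Dose on Day 6 |
|---|---|---|
| Arms A and B, main (days 1-5, 8-12) | yes | no |
| Arm C (days 1-5, 8-12, 15-19, 22-26) | yes | no |
| Arms A and B, day 1-10 alternative | yes | yes |

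On the first two rows, draws on Day 6 at the usual clock times fall 24, 25, 26, 28, 30 and 32 h after the Day 5 dose.

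**Step 2. Size of the error.** Inputs:

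- Half-life: about 10 h (Section 1.43) or about 9 h (Section 1.51).
- Tmax: 3 to 4 h after a single dose (Section 1.43).
- Dosing: once daily on Days 1-5.

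A quick hand check uses simple decay from the peak, 2^(-(t - Tmax)/half-life):

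- At 24 h: from 2^(-21/9) = 0.198 to 2^(-20/10) = 0.250.
- At 32 h: from 2^(-29/9) = 0.107 to 2^(-28/10) = 0.144.

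For the AUC I used a one-compartment oral model, scaled so that dose times bioavailability over volume equals 1:

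- ke = ln 2 / half-life.
- ka solves ln(ka/ke)/(ka - ke) = Tmax.
- Each dose contributes C(t) = [ka/(ka - ke)] × (e^(-ke·t) - e^(-ka·t)).
- The five daily doses are summed.

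| Half-life (h) | Tmax (h) | Day 5 AUC 0-8 h | Day 6 AUC, 24-32 h after the Day 5 dose | Ratio | Understatement |
|---|---|---|---|---|---|
| 9 | 3 | 6.533 | 1.221 | 0.187 | 81% |
| 9 | 4 | 6.209 | 1.286 | 0.207 | 79% |
| 10 | 3 | 7.028 | 1.550 | 0.221 | 78% |
| 10 | 4 | 6.718 | 1.617 | 0.241 | 76% |

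In the same model, Day 6 concentrations fall from 21-27% of the Day 5 peak at 24 h to 12-16% at 32 h. They only decline, so no absorption phase, Cmax or Tmax can be read from them.

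**Step 3. What remains usable, and is Day 4 a fair substitute?**

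- *Day 6 draw at the usual dosing time.* The modelled level is 1.0005 to 1.0010 times the Day 5 pre-dose level, so it is in effect the same 24 h trough.
- *Day 4 profile.* Day 4 is a dosing day in every arm and follows three daily doses. Section 1.43 says "steady-state was expected to be achieved after approximately 3 days of AZD1775 treatment in adult patients". The modelled Day 4 AUC 0-8 h is 99.87% to 99.94% of the Day 5 value, so moving one day earlier costs almost nothing.

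**The case against.** Several points on the other side stand.

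- **Day 5 is right.** Only the one-day tolerance is at fault, and it is sound for Arm A and B patients on the day 1-10 schedule. A held dose made up on Day 6 would also give a valid profile for that patient.
- **A mistimed series may be caught or never drawn.** The samples are defined relative to a dose, so a site may simply miss the profile. Section 14.22 puts visit and draw time on the tube label, and the Appendix II diary has a check mark for each day AZD1775 is taken, so an off-drug day should be visible. Neither item records the clock time of the dose, although forms not included in the documents might.
- **No frequency can be given.** The documents do not say how often the tolerance would be used, and they state no PK sample size. Biased summaries are a possibility, not an expectation.

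A reader might also infer more than the documents support:

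- *That every Day 6 sample is worthless.* Step 3 shows that the draw at the usual dosing time is a usable 24 h trough, provided the time of the last dose is known.
- *That the later-cycle samples need the same correction.* Those visits ask only for a pre-dose sample, which survives a one-day slip, and the tolerance is printed for Cycle 2 alone.
- *That exposure would be understated by more than 80% throughout.* Decay counted from the moment of dosing, 2^(-24/10) = 0.189 falling to 2^(-32/10) = 0.109, suggests this but ignores the protocol's own Tmax. The AUC comparison gives 76-78% at a 10 h half-life and 79-81% at 9 h.
- *That dose selection is compromised.* Section 7.7 bases the MTD on dose-limiting toxicity. The note in Section 8.11 lists PK among the grounds for exploring an intermediate level, but sets no PK threshold that this profile would drive.

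**Conclusion.** The point holds for the Cycle 1 post-dose samples on the main schedule of all three arms: the window permits Day 6, and there is no dose on Day 6 from which to time them. If a series were drawn anyway at the usual clock times, its AUC would be about 19-24% of the Day 5 AUC 0-8 h, an understatement of about 76-81%.

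That size rests on a one-compartment model with first-order absorption, full adherence on Days 1-5, half-life 9-10 h and Tmax 3-4 h. The calendar mismatch itself needs no model.

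This is a minor point. It is confined to the descriptive PK objective (2.31) and leaves the primary endpoint, the sample size and the error rates untouched.

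**What to change.** In Table 14.1, change the Cycle 1 profile window to Day 5 (-1 day), so that it is taken on Day 4 or Day 5. Keep +1 day only when AZD1775 is actually dosed on Day 6, as on the day 1-10 schedule. Leave the later-cycle pre-dose samples as they are. The change concerns sampling only and alters no dosing rule.

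The cost is one table entry and the matching line in the laboratory manual, with no added samples. One limit remains: for a Wednesday start, Days 4 and 5 fall on Saturday and Sunday, so a main-schedule patient would need a weekend draw or would have no profile. The present window does not solve that case either, because its Monday has no dose.

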15.0 Drug Information

15.1 AZD1775

- 15.11 Background: AZD1775 is a highly selective, adenosine-triphosphate (ATP) competitive, small molecule inhibitor of Wee1 kinase, that is involved in regulation of intra-S and G2 cell cycle checkpoints through phosphorylation and inhibition of CDK2 and CDK1, respectively. AZD1775 has significant selectivity over other tested protein kinases. In vitro, AZD1775 inhibits Wee1 activity and induces DNA damage as well as G2 checkpoint escape in cell based assays. AZD1775 increases cytotoxicity when used in combination with DNA damaging agents, such as gemcitabine, cisplatin, carboplatin and topotecan, in p53-deficient cell lines. In vivo, AZD1775 was well tolerated and showed enhancement of anti-tumor efficacy by gemcitabine, carboplatin, cisplatin, 5-fluorouracil (5-FU) and capecitabine in nude rat xenograft tumor models. Similarly, in nude mouse xenograft models, AZD1775 treatment resulted in significant tumor growth inhibition at tolerated doses, and also enhanced the anti-tumor growth effect of gemcitabine, carboplatin, and radiation therapy.
- 15.12 **Formulation**: AZD1775 is currently available as dry filled capsules for oral administration containing 25, 100 or 200 mg of AZD1775 with the following excipients: lactose, microcrystalline cellulose, croscarmellose sodium, and magnesium stearate.
- 15.13 **Preparation and storage**: Capsules are packaged in high density polyethylene (HDPE) bottles, and should be stored at room temperature, no more than 30° C. For further information, refer to the investigational product label. Provided by AstraZeneca.
- 15.14 Administration: 200 mg PO (or respective dose) once daily either 2 hours before or 2 hours after a meal
- 15.15 Pharmacokinetic information: The PK data of AZD1775 following a single oral administration showed a moderate rate of absorption with a Tmax occurring at 3 to 4 hours. Post-peak plasma concentrations declined essentially in a mono-exponential manner with a t1/2 in the region of 10 hours. Exposure as measured by maximum plasma drug concentration observed (Cmax) and area under the curve (AUC)0-∞ increased in a doseproportional manner over the dose range of 325 to 1300 mg. Following single (100 to 325 mg) and multiple dose administrations of AZD1775 (25 to 325 mg BID and 100 to 200 mg once daily [QD]) with carboplatin, cisplatin, and gemcitabine, plasma exposure of AZD1775 was consistent with predictions based on the single-dose regimen. AZD1775 was moderately bound to plasma proteins in all species tested, with the unbound fractions (at AZD1775 concentration of 1 µM) in plasma from the rat, dog and human being 23.2, 40.0, and 39.5%, respectively. Binding to plasma proteins was independent of AZD1775 concentration (0.1-10 μ M) in the rat and human, but an increase in unbound fraction from 30.6% at 0.1 µM to 45.4% at 10 µM was observed in the dog. CYP3A4 is the

major CYP isoform involved in the oxidative metabolism of AZD1775, to the N-demethylated product. In addition, studies with flavin-containing monooxygenase (FMO) enzymes indicated that FMO3 and FMO5 were involved in formation of the N-oxide derivative of AZD1775.

- 15.16 **Potential Drug Interactions**: The following treatments and all the medications listed in Appendix VI are prohibited while in this study. Any further questions regarding concomitant treatments should be referred to the sponsor:
- No other investigational therapy should be given to patients. No anticancer agents other than the study medications should be given to patients. If such agents are required for a patient, then the patient must first be withdrawn from the study.
- No formal clinical drug interaction studies have been performed with AZD1775. An exploratory assessment of the effect of aprepitant on AZD1775 exposure in oncology patients suggests that there is a drug interaction between AZD1775 and aprepitant, as exposure to AZD1775 increased by ~60% when aprepitant was co-administered with AZD1775. The observed increase in AZD1775 exposure is likely the result of CYP3A4 inhibition by aprepitant. This increase in exposure is statistically significant. At the selected MTDs, this increase may also be of clinical importance. Therefore, concomitant treatment with aprepitant and fosaprepitant is not allowable per protocol until further evaluation.

Potent or moderate inhibitors or inducers of CYP3A4, sensitive CYP3A4 substrates, and CYP3A4 substrates with a narrow therapeutic window should be avoided until additional data on drug-drug interaction becomes available (Appendix VI).

- In vitro data suggests that AZD1775 may also be a weak reversible inhibitor of CYP2C19. Caution should be exercised with concomitant administration of AZD1775 and agents that are sensitive substrates of CYP2C19, or substrates of this enzyme with narrow therapeutic range; refer to Appendix VI for a list of sensitive substrates of CYP2C19, or substrates of this enzyme with narrow therapeutic range.
- AZD1775 has been shown to be a weak inducer of CYP1A2 *in vitro* with a maximum measured response between donors of 39.9% to 93.1% (at 10 μ M) and 18.6% to 32.5% (at 5 μ M) of the positive control omeprazole (50 μ M), respectively. Given the nature of the AZD1775 dosing schedule, however, the risk of induction in the clinic is considered low. No specific precautions are recommended at this time, except to be initially vigilant when using substrates of CYP1A2 with a narrow therapeutic range.
- *In vitro* studies have shown that AZD1775 may be a substrate and inhibitor for human P-glycoprotein (P-gp). Caution should be exercised when agents that are inhibitors or substrates of P-gp are administered concomitantly with AZD1775 (see Appendix VI).
- Recent *in vitro* transporter studies have shown AZD1775 to be an inhibitor of BCRP (IC50 5.1 μM). This finding is particularly relevant for drugs administered orally where exposure is normally limited by BCRP-mediated efflux, in particular some statins. Modelling has predicted a substantial increase in the exposure of Atorvastatin when co-administered with AZD1775 and the

use of Atorvastatin is therefore prohibited in the current study. Other drugs where the disposition is mediated via BCRP should be administered with caution, dose modification considered or substituted by an alternative drug (Appendix VI).

- AZD1775 has been shown to be an inhibitor or MATE1 and MATE2K transporters. A drug interaction with substrates of either transporter cannot be ruled out, the most important substrate known to date being **metformin**.
- Herbal preparations/medications are not allowed throughout the study. These herbal medications include, but are not limited to: St. John's wort, kava, ephedra (ma huang), gingko biloba, dehydroepiandrosterone (DHEA), yohimbe, saw palmetto, and ginseng. Patients should stop using these herbal medications 14 days prior to first dose of AZD1775.
 - 15.17 **Known potential toxicities**: Based on the preliminary safety data available, the most frequent adverse events observed were blood and lymphatic disorders (anemia, febrile neutropenia), gastrointestinal disorders (diarrhea, vomiting, nausea, abdominal pain, constipation), general disorders and administration site conditions (fatigue, fever, chills), and investigation findings (thrombocytopenia, neutropenia, hematology and serum chemistry).
 - 15.18 **Drug procurement:** Drug will be provided by AstraZeneca.

15.2 Cytarabine (AraC)

- 15.21 **Background**: Cytarabine (cytosine arabinoside) inhibits DNA synthesis. Cytosine gains entry into cells by a carrier process, and then must be converted to its active compound, aracytidine triphosphate. Cytosine is a pyrimidine analog and is incorporated into DNA; however, the primary action is inhibition of DNA polymerase resulting in decreased DNA synthesis and repair. Cytarabine is specific for the S phase of the cell cycle (blocks progression from the G1 to the S phase).
- 15.22 **Formulation**: Commercially available for injection, powder for reconstitution: 100 mg, 500 mg, 1 gram, 2 gram
- 15.23 **Preparation, storage, and stability**: Store intact vials of powder at room temperature 15°C to 30°C (59°F to 86°F). Reconstitute with bacteriostatic water for injection. Reconstituted solutions are stable for up to 8 days at room temperature, although the manufacturer recommends use within 48 hours. Further dilution in 250-1000 mL of D5W or 0.9% NaCL is stable for 8 days at room temperature (25C). Note: Solutions containing

bacteriostatic agents should not be used for the preparation of either high doses or intrathecal doses of cytarabine.

15.24 Administration: Low-dose cytarabine (LD-AraC) will be administered at a starting dose of 20 mg BID subcutaneously (sc) for 10 days of a 28-day cycle., with dosing adjustments as outlined in section 8.

15.25 **Pharmacokinetic information**:

Distribution: V_d : Total body water; widely and rapidly since it enters the cells readily; crosses blood-brain barrier with CSF levels of 40% to 50% of plasma level

Metabolism: Primarily hepatic; metabolized by deoxycytidine kinase and other nucleotide kinases to aracytidine triphosphate (active); about 86% to 96% of dose is metabolized to inactive uracil arabinoside.

Half-life elimination: I.V.: Initial: 7-20 minutes; Terminal: 1-3 hours. **Excretion**: Urine (~80%) within 24 hours.

15.26 **Potential Drug Interactions**:

Decreased Effect: Cytarabine may decrease the effect of Flucytosine; cytarabine may decrease digoxin absorption.

15.27 **Known potential adverse events:** Consult the package insert for the most current and complete information.

Warnings/Precautions: Potent Myelosuppressive agent Common known potential toxicities, frequency not defined: Other: Fever

Dermatologic: Rash Gastrointestinal: Anal inflammation, anal ulceration, anorexia, diarrhea, mucositis, nausea, vomiting Hematologic: Myelosuppression, neutropenia, anemia, thrombocytopenia, bleeding, leukopenia, megaloblastosis, reticulocytes decreased Hepatic: Hepatic dysfunction, transaminases increased (acute) Local: Thrombophlebitis

Less common known potential toxicities:

Cardiovascular: Chest pain, pericarditis Central nervous system: Dizziness, headache, neural toxicity, neuritis Dermatologic: Alopecia, pruritus, skin freckling, skin ulceration, urticaria Gastrointestinal: Abdominal pain, bowel necrosis, esophageal ulceration, esophagitis, pancreatitis, sore throat Genitourinary: Urinary retention Hepatic: Jaundice Local: Injection site cellulitis Ocular: Conjunctivitis Renal: Renal dysfunction Respiratory: Dyspnea Miscellaneous: Allergic edema, anaphylaxis, sepsis

Infrequent and/or case reports:

Amylase increased, aseptic meningitis, cardiopulmonary arrest (acute), cerebral dysfunction, cytarabine syndrome (bone pain, chest pain,

conjunctivitis, fever, maculopapular rash, malaise, myalgia); exanthematous pustulosis, hyperuricemia, injection site inflammation (SubQ injection), injection site pain (SubQ injection), interstitial pneumonitis, lipase increased, paralysis, rhabdomyolysis, veno-occlusive liver disease

15.28 **Drug procurement:** Commercial supplies. Pharmacies or clinics shall obtain supplies from normal commercial supply chain or wholesaler.

